1.1 INTRODUCTION

A Case Control Etiologic Study of Sarcoidosis (ACCESS) is a multicenter study sponsored by the National Heart, Lung and Blood Institute (NHLBI). The study is a case control study to investigate the etiology of sarcoidosis. The primary investigation is the study of etiology in which 720 patients with sarcoidosis representing both men and women, white and minority race/ethnicity and the spectrum of disease severity will be enrolled as will 720 age, gender and race/ethnicity matched controls recruited through random digit dialing to represent the general population. A prospective cohort study of the first 240 cases enrolled in the case control study will be used to define categories of outcome that may be related to the etiology of sarcoidosis and to describe the clinical course of sarcoidosis.

Sarcoidosis is a systemic granulomatous disease of unknown etiology. The organ systems most frequently of concern in sarcoidosis are the respiratory system (especially the lower respiratory tract, but also the large airways and upper respiratory tract), the eyes and the skin; involvement of the liver, nervous system, kidneys and the musculoskeletal system may be found. Sarcoid inflammation in vital organs (e.g., lungs, heart or nervous system) can be fatal, but for most patients the clinical course is benign.

Ten clinical centers, located at major medical centers/hospitals in the United States, are responsible for screening and recruitment of eligible sarcoidosis cases and matched controls. The ACCESS Clinical Coordinating Center is responsible for the study's statistical design, data collection and management, and analysis of study results. The Project Office, located in the Lung Biology and Disease Program of the Division of Lung Diseases at the NHLBI, is responsible for the overall direction and administration of ACCESS in collaboration with the Study Chairman, who was appointed by the NHLBI Director. A central repository for storage of case and control specimens is operated by McKesson Bioservices under a contract with the NHLBI. Specialized Core Laboratories also participate in the study.

1.2 OBJECTIVES

The case control study is designed to investigate possible causes and risk factors for sarcoidosis. Evaluation of cases and controls to determine the etiology of sarcoidosis will include an inquiry into environmental and occupational exposures, family history, medical history, and collection of blood specimens. Blood specimens will be used to identify potential immunogenetic and infectious contributions to sarcoidosis by means of specialized studies involving recently developed microbiology and nucleic acid analysis techniques such as HLA Class II marker studies, mycobacterial studies, immunogenetic studies, differential display polymerase chain reaction (PCR) studies, and comparisons of nucleic acid sequences from blood specimens to those of known pathogens. Bronchoalveolar lavage studies will also be performed. Specific hypotheses concerning the cause of sarcoidosis will address infections, genetic factors, and occupational or environmental factors as potential risk factors for sarcoidosis.

The clinical course study of 240 cases is designed to: (1) define sarcoidosis cases that do or do not clinically resolve over a two-year period of follow-up, and (2) develop a clinical / radiological / physiologic sarcoidosis assessment system for reporting the severity of disease.

1.3 STUDY RATIONALE

In spite of the advances in research on the cellular mechanisms of sarcoidosis, the underlying causes remain unknown. There may be some overlap between sarcoidosis and other granulomatous disease of unknown etiology (e.g., primary biliary cirrhosis and Crohn's disease), but these insights are of little help in determining the etiology of sarcoidosis (Spiteri et al, 1992). Recurrence of granulomatous lesions in sarcoidosis patients after lung transplantation also provides insight, but does not lead to clear conclusions as to specific etiologies (Bjørtuft et al, 1994; Johnson et al, 1993; Martinez et al, 1994).

Etiologies including infectious agents such as mycobacteria (Mitchell et al, 1992; Fidler et al, 1993), lifestyle habits such as pica (clay eating and starch eating) (Comstock et al, 1961), place of residence (rural versus other) and environmental exposures such as pine pollens and occupational

exposures (Comstock et al, 1961; Cummings et al, 1959; Douglas, 1961; Dunner and Williams, 1961; Gentry et al, 1955; Horwitz, 1961; Keller, 1971; Nobechi, 1969; Sartwell, 1983; Teirstein and Lesser, 1983) have been investigated in clinical studies of sarcoidosis. But no credible etiologic agent has been identified. Rural residence has been associated with sarcoidosis (Buck, 1961; Buck and McKusick, 1961; Buck and Sartwell, 1961; Gentry et al, 1955), but some investigators suspect this association is a result of confounding (Sartwell, 1983; Teirstein and Lesser, 1983). The most compelling observation has been an unquantitated but striking familial aggregation found in the classic case control studies of Buck, Sartwell and McKusick (Buck, 1961; Buck and McKusick, 1961; Buck and Sartwell, 1961). The main shortcomings in all of the case control studies, including those of Buck and colleagues, have been the small number of cases and controls (Buck studied 62 cases), and possible biases in selection of controls.

Sarcoidosis has been well characterized pathologically, and the most interesting research results in recent years have addressed the cellular mechanisms of disease activity. Conclusions about etiologic factors that would be of use in treatment or primary prevention of sarcoidosis have been difficult to reach. Previous studies of the etiology and natural history of sarcoidosis in the United States, especially in black patients in the United States, have been limited by relatively small numbers of patients. Recent advances in laboratory methods (e.g., polymerase chain reaction technology), control selection and statistical analysis methods (e.g., methods for random digit dialing and synthetic case control data analysis) will be of use to address the etiology of sarcoidosis. Promising leads to the etiology of sarcoidosis have come from diverse sources: in clinical laboratory investigations alveolitis has been found to precede granulomatous inflammation; in case control studies familial aggregation has been identified; and in case reports recurrence of granulomatous inflammation has been observed after lung transplantation. Thus, it is appropriate now to identify a large number of patients with sarcoidosis, establish disease stage using standardized criteria, select an appropriate control for each case, and use case control methods to search for exposures or genetic predispositions which could cause alveolitis, exposures or genetic predispositions that would aggregate in families, and exposures or genetic predispositions

that would result in recurrence of sarcoid granulomas in transplanted lungs. The answer is not likely to prove to be a single, known exposure. An interaction of exposures with a genetic predisposition would be of great interest.

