1.6 ANALYSIS PLANS

Although the etiology study includes as possible etiological agents a wide range of environmental, infectious, genetic, and sociodemographic exposure variables, the analytical plans for all of these agents are similar. Except for certain genetics studies, a matched case control design is used to identify those exposures or variables that have different prevalences or quantitative levels between cases and controls. Once identified, multivariate models are used to determine if the list of possible etiological agents can be further reduced to those that provide unique contributions to the risk equation. It is expected that matched-pair logistic regression will be used for these determinations.

It is planned to determine if different defined subgroups of the ACCESS population have different profiles of progression or regression of the disease over the course of two years. Analytical techniques for the clinical course study will include analysis of variance, regression, life table analyses, and standard analyses for categorical variables.

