Sarcoidosis may be a disease in which there is an interplay between multiple genetic and environmental factors. Elucidating these factors may be difficult because of the etiologic heterogeneity. The disease may aggregate but does not segregate in families. Thus, the genetic abnormalities in sarcoidosis may be predisposing but not predetermining. For diseases such as sarcoidosis, if a specific gene is found to have a large role in the disease, and thus might be of etiologic importance, it may only account for a small proportion of the attributable risk.

Two basic approaches are available for identifying genetic causes of disease. One begins with documentation of familial aggregation, followed by segregation analysis, linkage analysis, and finally ends with molecular cloning of the gene. The other approach tests candidate genes. In case control studies, associations between genetic and environmental factors can be observed in cases compared to controls, and interactions between genetic and environmental factors can be tested. Both approaches would appear to be important in elucidating the genetic predisposition to sarcoidosis. In the proposed case control study, we will be able to study candidate genes during the course of the study. In addition, we plan to store specimens from sarcoidosis cases and controls for future studies of any candidate genes, such as may be determined by familial aggregation studies.

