3.6.1 HLA Typing in Sarcoidosis

ACCESS will investigate HLA Class II associations with sarcoidosis and correlate any associations with the environmental history to identify possible causative agents. PCR with sequence specific oligonucleotide (SSO) probes will be used to determine the molecular sequence of HLA Class II DR, DQ and DP beta genes from cases with newly diagnosed sarcoidosis and controls. Any genes that can not be identified using SSO probes will be cloned and sequenced. The specific aims are:

- A. Determine which alleles are associated with sarcoidosis and which alleles are protective.
- B. Determine which amino acids in the pockets that bind antigenic peptides are associated with sarcoidosis and which are protective.
- C. Determine interactions between alleles or amino acids in the binding pockets that are associated with sarcoidosis and specific environmental exposures such as exposure to metals and infectious agents.
- D. Determine whether alleles or amino acids in the binding pockets that are associated with sarcoidosis are also associated with specific clinical syndromes (e.g., erythema nodosum, extrapulmonary sarcoidosis, persistent sarcoidosis) among cases.

The case control design is the ideal method to investigate relationships between genetic and environmental factors in disease. Class II molecules are known to be involved in sarcoidosis -- both from the presumed pathophysiology and genetic studies. If specific alleles or amino acids in the binding pockets are found to be associated with sarcoidosis, informative next steps would be immunoprecipitation of Class II molecules with bound antigenic peptide and identification of the
possible etiologic agents that contain those peptides because they may be the etiologic agents of sarcoidosis.

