Tables 1 and 2 show the power of the proposed design to detect specified odds ratios as a function of the correlation (0.5 and 0.0) between case and control exposure rates, and the expected value of the control exposure rate with the alpha level for the test set at 0.05 (two sided test) and with 720 cases. With the proposed number of cases and controls there will be 98.6% power to detect odds ratios of 0.7 or less and 98.8% power to detect odds ratios of 1.4 or greater when the correlation between case and control exposures is 0.5 (Table 1) and the proportion of controls exposed is 0.3. If the correlation between cases and control exposures is 0.0 (a conservative estimate), the power is reduced to 84.3% and 85.1%, respectively. If the proportion of controls exposed is reduced to 0.05 there is at least 90% power to detect an odds ratio of 2.0.

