factor also present and at the same level of magnitude in males or is it different. For binary exposure variables a matched case control regression model will be used with terms for the subgroup, the exposure, and the exposure-subgroup interaction in the model. For a case control design with one case and one control, the Cox Proportional Hazards model can be used by creating a dummy variable that always lists the case and "failing" first with control "censored" after the case "failure time". Power calculations for the factorial term in the Cox Model have been published (Peterson and George, 1993). In general the statistical efficiency of the interaction test is lower than the main effects test. For instance, with 50% of the population in one subgroup and 50% in the complimentary subgroup, the efficiency of the interaction test is one half that of the main effects test.

As an example, the current study design has at least 80% percent power to detect an odds ratio of 1.25 when the exposure variable of interest has a 30% prevalence and the test is being performed at the 5% alpha level. Now let us consider a statistical interaction test of an exposure between two groups. The test would be designed to determine if the ratio of the two odds ratios in the two groups were different or the same. Specifically, the interaction test is a test of whether the ratio of these two odds ratios is one. To be able to detect a ratio of the two odds ratios that is 1.25 or larger with 80% power with an exposure variable with a 30% prevalence and testing at the 5% alpha level would require twice the number of case control pairs or 1,440 cases. With 720 cases, there is at least 80% power to detect a ratio of two odds ratios on the order of magnitude of 1.38. This is not substantially different from the operating characteristics of the main effect comparisons. Thus there will be adequate power to detect small interactions with the proposed sample size.

For continuous variables, there is little impact on the power of proposed analyses to detect meaningful differences between case and control means in each of the above subgroup sizes. With 180 cases in a subgroup, it will be possible to detect differences of 0.34 standard deviations with 90% power when testing at alpha 0.05 (two sided test).

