Statistical analyses for probability inference based on these estimates can also be performed using conditional logistic regression (Breslow et al, 1978). This model is robust in the sense that it will allow for the inclusion of effect modifiers or risk factors. Effect modifiers are variables that change the exposure-risk odd ratios for the disease. It will not be possible to estimate odds ratios for age, gender, or race since these are matching variables. However, it will be possible to include interaction terms between gender, race, or age and other exposure variables to determine if the odds ratio estimates for these other variables are homogenous in males and females or blacks and whites. In some situations, analyses will be required to determine if one type of exposure (e.g., occupational) is associated with a genetic predisposition of sarcoidosis. These analyses will be done using the conditional logistic regression model in a matched case control format. Tests of the effect modification of the exposure will be done using an interaction variable in the conditional logistic model. Conditional logistic regression will be performed using the PHREG procedure in SAS.

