12.3.3 Analyses of ACCESS Substudies

All of the proposed analysis plans for the ACCESS Substudies are identical to the plans presented in Section 12.3.2. Only the sample sizes may change and this was addressed in Section 12.2.

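### Section 12.2.3 overstates interaction power: for two equal subgroups efficiency is one quarter, not one half, and the gene-by-exposure term has only about 9% to 29% power at the ratio of 1.38 given as detectable

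*Protocol*

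**What the plan says.** The protocol returns to gene-by-exposure interaction several times. The rationale (1.3) says "An interaction of exposures with a genetic predisposition would be of great interest". Section 2.2 says that in case control studies "interactions between genetic and environmental factors can be tested". The third aim of the HLA study (3.6.1) is to "Determine interactions between alleles or amino acids in the binding pockets that are associated with sarcoidosis and specific environmental exposures".

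The test is named in 12.3.2.2: "Tests of the effect modification of the exposure will be done using an interaction variable in the conditional logistic model". Section 12.3.3 extends this: "All of the proposed analysis plans for the ACCESS Substudies are identical to the plans presented in Section 12.3.2". Section 1.6 has an exception, "Except for certain genetics studies, a matched case control design is used", but names no other analysis for those studies.

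Interaction power is covered only in 12.2.3. With the population split equally, the interaction test is said to have half the efficiency of the main-effect test. From a main-effect odds ratio of 1.25 (30% exposure, 5% alpha, at least 80% power), the section concludes that an interaction ratio of 1.25 would need 1,440 pairs, and that 720 pairs give at least 80% power for a ratio of about 1.38. It ends: "Thus there will be adequate power to detect small interactions with the proposed sample size".

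**The concern.** The factor of one half describes estimating an effect within one of two equal subgroups. It does not describe comparing the two subgroups, which carries the sampling error of both. If the factor is wrong, so are the 1,440 pairs, the 1.38 and the closing assurance.

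The example also concerns a subgroup factor that splits the population evenly. An HLA allele and an occupational or environmental exposure both vary within matched pairs, and both may be uncommon. No power is given for that case, although it is a named aim. A null HLA-by-exposure result would be read against an assurance of power that the design does not have.

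**Working it through.** **Inputs from the protocol.** 720 pairs, one control per case; "alpha level for the test set at 0.05 (two sided test) and with 720 cases"; exposure 30% in controls; correlation r of 0.5 or 0 between case and control exposure, as in Tables 1 to 12. The protocol gives no allele frequencies, so those below are assumptions.

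**Step 1: reproduce the protocol's figures.** The 12.2.1 formula with one control per case is power = Φ(δ√N/√ψ − 1.96), with δ = p1 − p0 and ψ = p1 + p0 − 2p1p0 − 2r√(p0q0p1q1).
- Odds ratio 1.4: p1 = 0.375, δ = 0.075. Power is 0.988 at r = 0.5 and 0.851 at r = 0, matching Tables 1 and 2.
- Odds ratio 1.25: 79.6% at r = 0.5, but 50.7% at r = 0. The 80% benchmark therefore uses r = 0.5.
- Interaction ratio at efficiency one half: exp(√2 × ln 1.25) = 1.37, close to the stated 1.38. Power at 1.38 is then about 81% at r = 0.5.

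So the stated figure reproduces, but only with both r = 0.5 and the one-half factor.

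**Step 2: efficiency for two equal subgroups.** Let V be the variance of the log odds ratio from all 720 pairs. Each half (360 pairs) has variance 2V. The difference between halves has variance 2V + 2V = 4V. Efficiency is V/4V = 1/4; one half is V/2V, the figure for one subgroup alone.

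Testing an interaction ratio in 720 pairs is therefore like testing a main effect of that size in 180 pairs, not 360. The protocol's tables show the consequence at 30% exposure and a value of 1.4: Table 5 (360 pairs, r = 0.5) gives 0.846, Table 7 (180 pairs, r = 0.5) 0.558, and Table 8 (180 pairs, r = 0) 0.323.

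**Step 3: corrected figures at 30% exposure.**
- Ratio 1.38: δ = 0.0716. Main-effect z = 4.03 (r = 0.5) or 2.87 (r = 0). Halving z for efficiency one quarter gives Φ(2.02 − 1.96) = 52% and Φ(1.43 − 1.96) = 30%.
- Ratio equivalent to a main-effect odds ratio of 1.25: exp(2 × ln 1.25) = 1.25² = 1.56.
- Pairs needed for an interaction ratio of 1.25: 4 × 720 = 2,880, not 1,440.

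**Step 4: gene-by-exposure term.** The model has gene, exposure and their product. Assumptions: no main effects, gene and exposure independent in controls, no within-pair correlation. The information is N Σ P(case in cell i) P(control in cell j) w(1 − w) dd′, where d is the difference in covariates and w = θi/(θi + θj), with θ the cell's odds ratio. The interaction variance is the last diagonal element of the inverse. The case-only variance is the sum of 1/n over the four case cells.

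Example, allele 10%, exposure 10%, ratio 1.38: about 7 of 720 controls carry both factors. The matched variance is 0.305, so z = 0.322/0.553 = 0.58 and two-sided power is 9%. Expected case cells are 581.0, 64.6, 64.6 and 9.9; the case-only variance is 0.134 and power 14%.

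| Allele | Exposure | Ratio | Matched term | Case-only | Variance, case-only/matched |
|---|---|---|---|---|---|
| 10% | 10% | 1.38 | 9% | 14% | 0.44 |
| 20% | 30% | 1.38 | 21% | 40% | 0.46 |
| 30% | 30% | 1.38 | 26% | 48% | 0.47 |
| 50% | 30% | 1.38 | 29% | 53% | 0.49 |
| 10% | 10% | 3 | 59% | 97% | 0.32 |
| 20% | 10% | 2 | 41% | 79% | 0.39 |
| 20% | 30% | 2 | 72% | 97% | 0.43 |
| 30% | 30% | 2 | 82% | 99% | 0.44 |

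The 29% at 50%/30% agrees closely with the 30% in Step 3 for equal subgroups at r = 0.

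**Step 5: limits of case-only.** With no interaction but an allele-exposure odds ratio of 1.2 in the source population (30%/30%, 720 cases), its false-positive rate is 18%; at 1.5 it is 65%. A test for an allele-exposure odds ratio of 1.5 in 720 controls has only 20% power at 10%/10% and 54% at 20%/30%.

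**The case against.** The strongest objection is that the planned test is valid. The matched interaction term needs no assumption that gene and exposure are independent, and omitting a second, assumption-dependent analysis is not an error. Such an analysis could also sit in an analysis plan that is not shown. All of that stands, so the case-only suggestion is optional. It does not touch the power statement, which is in the protocol and is arithmetically wrong.

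Independence is also doubtful here. Section 12.1 notes that some alleles are not shared by black and white participants. As an assumed illustration, pooling two races equally with allele frequencies 10% and 30% and exposures 20% and 40% gives a 31% case-only false-positive rate unless race is adjusted for. Matching uses only three race categories, so ancestry within a category may link allele and exposure. HLA affects immune response (2.2), so it may also affect recorded infection history. These points stand and limit where case-only can be used.

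A reader might infer that the matched term always has about half the power of a case-only test. It does not: the gap narrows to 82% versus 99% at 30%/30% with a ratio of 2. What is roughly stable is the variance, at about half or less. A reader might also infer that 720 typed controls are available for checking independence. Section 3.6.1 gives no number typed; the immunogenetics study (3.6.7) plans 360 pairs.

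**Conclusion.** The interaction-power statement in 12.2.3 is wrong on its own terms. For two equal subgroups at 30% exposure, 720 pairs give about 52% power (r = 0.5) or 30% (r = 0) at a ratio of 1.38, not at least 80%. The 52% and 30% depend only on the protocol's formula and the one-quarter efficiency.

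For the gene-by-exposure aim, power at 1.38 is about 9% to 29%. That range assumes alleles at 10% to 50%, exposures at 10% to 30%, no main effects, no within-pair correlation and all 720 pairs typed; fewer typed pairs would lower it. Larger ratios with common factors remain detectable, so the documents do not support saying that such interactions would generally be missed. Nor do they support replacing the matched term with a case-only analysis.

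**What to change.** In 12.2.3, replace the efficiency of one half by one quarter, 1,440 pairs by 2,880, and 1.38 by about 1.56, and state that these figures use a correlation of 0.5. Add the values at correlation 0. Withdraw the concluding sentence on small interactions. Then give gene-by-exposure power separately for the term in 12.3.2.2, over a stated range of allele and exposure frequencies and for the number of pairs actually typed.

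Optionally, in 12.3.2.2 and 3.6.1, add a case-only estimate beside the matched term, labelled as a sensitivity analysis: regression of allele carriage on exposure among typed cases, adjusted for race, gender, age and Clinical Center. Show the allele-exposure association in controls with its confidence interval; do not take a non-significant test as proof of independence. Do not rely on case-only for infectious exposures, or where ancestry within a race category may link allele and exposure.

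The cost is a few lines of text and code, with no new data and no change in sample size. The price is a more modest claim about interactions.
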